6.3. Follow-up

6.3.1. Follow-up Visit

Subjects will return to the CRU for follow-up visit at the discretion of the principal investigator (PI) or if the subject withdraws consent or if there are unresolved AE at discharge. At this visit, the following procedures may include, but are not limited to:

- Conduct limited PE and weight measurement.
- The investigator or his/her designee will discuss with the subject the need to use highly effective contraception consistently and correctly according to the contraception guidelines and will confirm highly-effective, proper contraception is being used.
- Assess supine BP and pulse rate.

- Obtain information regarding the use of concomitant treatment and the occurrence of AEs.
- Review concomitant treatments.

6.4. Follow-up Contact

Follow-up contact will be completed at least 28 calendar days after the last administration of the investigational product to capture any potential adverse events (see [Section 8.1.4](#)) and to confirm appropriate contraception usage (see [Section 4.3.4](#)). Contact with the subject may be done via a phone call.

6.5. Subject Withdrawal /Early Termination

Withdrawal of consent:

Subjects who request to discontinue receipt of study treatment will remain in the study and must continue to be followed for protocol-specified follow-up procedures. The only exception to this is when a subject specifically withdraws consent for any further contact with him or her or persons previously authorized by the subject to provide this information. Subjects should notify the investigator in writing of the decision to withdraw consent from future follow-up, whenever possible. The withdrawal of consent should be explained in detail in the medical records by the investigator, as to whether the withdrawal is only from further receipt of investigational product or also from study procedures and/or posttreatment study follow-up, and entered on the appropriate case report form (CRF) page. In the event that vital status (whether the subject is alive or dead) is being measured, publicly available information should be used to determine vital status only as appropriately directed in accordance with local law.

Lost to follow-up:

All reasonable efforts must be made to locate subjects to determine and report their ongoing status. This includes follow-up with persons authorized by the subject as noted above. All attempts should be documented in the subject's medical records. If it is determined that the subject has died, the site will use locally permissible methods to obtain the date and cause of death. If the investigator's use of a third-party representative to assist in the follow-up portion of the study has been included in the subject's informed consent, then the investigator may use a sponsor-retained third-party representative to assist site staff with obtaining the subject's contact information or other public vital status data necessary to complete the follow-up portion of the study. The site staff and representative will consult publicly available sources, such as public health registries and databases, in order to obtain updated contact information. If, after all attempts, the subject remains lost to follow-up, then the last-known-alive date as determined by the investigator should be reported and documented in the subject's medical records.

Subjects may withdraw from the study at any time at their own request, or they may be withdrawn at any time at the discretion of the investigator or sponsor for safety (see [Section 8.1.3](#)) or behavioral reasons, or the inability of the subject to comply with the

protocol-required schedule of study visits or procedures at a given investigator site. The early termination visit applies only to subjects who are randomized and then are prematurely withdrawn from the study.

If a subject does not return for a scheduled visit, every effort should be made to contact the subject. The investigator or site staff should attempt to contact the subject twice. After 2 attempts, CRU staff may send a registered letter. If no response is received from the subject, the subject will be considered lost to follow-up. All attempts to contact the subject and information received during contact attempts must be documented in the subject's medical record. In any circumstance, every effort should be made to document subject outcome, if possible. The investigator should inquire about the reason for withdrawal, request that the subject return for a final visit, if applicable, and follow up with the subject regarding any unresolved AEs.

It may be appropriate for the subject to return to the clinic for final safety assessments to be scheduled as early as practically feasible following the decision to withdraw from the study. Subjects should be questioned regarding their reason for withdrawal. At the early-withdrawal visit, every effort must be made to complete the following assessments:

- Limited PE, if there is a new or open AE or clinically significant abnormal physical finding from the last visit;
- Supine BP and pulse rate measurements;
- Triplicate 12-lead ECG measurement;
- Blood and urine specimens for safety laboratory;
- Blood sample for PK analysis.

Lack of completion of all or any of the withdrawal/early termination procedures will not be viewed as protocol deviations so long as the subject's safety was preserved.

If the subject withdraws from the study and also withdraws consent for disclosure of future information, no further evaluations should be performed and no additional data should be collected. The sponsor may retain and continue to use any data collected before such withdrawal of consent.

Subjects who withdraw from the study may be replaced at the discretion of the investigator upon consultation with the sponsor.

7. ASSESSMENTS

Every effort should be made to ensure that protocol-required tests and procedures are completed as described. However, it is anticipated that from time to time there may be circumstances outside the control of the investigator that may make it unfeasible to perform the test. In these cases, the investigator must take all steps necessary to ensure the safety and well-being of the subject. When a protocol-required test cannot be performed, the investigator will document the reason for the missed test and any corrective and preventive

actions that he or she has taken to ensure that required processes are adhered to as soon as possible. The study team must be informed of these incidents in a timely manner.

For samples being collected and shipped, detailed collection, processing, storage, and shipment instructions and contact information will be provided to the investigator site prior to initiation of the study.

7.1. Safety

7.1.1. Laboratory Tests

The following safety laboratory tests will be performed at times defined in the **STUDY PROCEDURES** section of this protocol. Additional laboratory results may be reported on these samples as a result of the method of analysis or the type of analyzer used by the clinical laboratory; or as derived from calculated values. These additional tests would not require additional collection of blood. Unscheduled clinical laboratory measurements may be obtained at any time during the study to assess any perceived safety concerns.

Table 5. Safety Laboratory Tests

| Hematology | Chemistry | Urinalysis | Other |
|-------------------------------|-------------------------------------|-------------------------|-----------------------|
| Hemoglobin | BUN/urea and creatinine | pH | FSH ^b |
| Hematocrit | Glucose (fasting) | Glucose (qual) | Urine drug screening |
| RBC count | Calcium | Protein (qual) | Hepatitis B surface |
| MCV | Sodium | Blood (qual) | antigen ^c |
| MCH | Potassium | Ketones | Hepatitis B core |
| MCHC | Chloride | Nitrites | antibody ^c |
| Platelet count | Total CO ₂ (bicarbonate) | Leukocyte esterase | Hepatitis C core |
| WBC count | AST, ALT | Urobilinogen | antibody ^c |
| Total neutrophils (Abs) | Total bilirubin | Urine bilirubin | HIV ^c |
| Eosinophils (Abs) | Alkaline phosphatase | Microscopy ^a | |
| Monocytes (Abs) | Uric acid | | |
| Basophils (Abs) | Albumin | | |
| Lymphocytes (Abs) | Total protein | | |
| | Lipase | | |
| | Amylase | | |
| Additional Tests | | | |
| (Needed for Hy's Law): | | | |
| AST, ALT (repeat) | | | |
| Total bilirubin (repeat) | | | |
| Albumin (repeat) | | | |
| Alkaline phosphatase (repeat) | | | |
| Direct bilirubin | | | |
| Indirect bilirubin | | | |
| Creatine kinase | | | |
| GGT | | | |
| PT/INR | | | |

^a Only if urine dipstick is positive for blood, protein, nitrites or leukocyte esterase.

^b At Screening only, in females who are amenorrheic for at least 12 consecutive months.

^c At Screening only.

- The minimum requirement for drug screening includes cocaine, tetrahydrocannabinol (THC), opiates/opioids, benzodiazepines, and amphetamines.
- Subjects may undergo random urine drug testing at the discretion of the Investigator. Drug testing conducted prior to dosing must be negative for subjects to receive investigational product.

CCI

7.1.2. Physical Examinations

Physical examinations may be conducted by a physician, trained physician's assistant, or nurse practitioner as acceptable according to local regulation. A full physical examination will include head, ears, eyes, nose, mouth, skin, heart and lung examinations, lymph nodes, and gastrointestinal, musculoskeletal, and neurological systems. The limited or abbreviated physical examination will be focused on general appearance, the respiratory and cardiovascular systems, and subject-reported symptoms.

For measuring weight, a scale with appropriate range and resolution is used and must be placed on a stable, flat surface. Subjects must remove shoes, bulky layers of clothing, and jackets so that only light clothing remains. They must also remove the contents of their pockets and remain still during measurement of weight.

7.1.3. Blood Pressure and Pulse Rate

BP and pulse rate will be measured at times specified in the **SCHEDULE OF ACTIVITIES** section of this protocol. Additional collection times, or changes to collection times, of BP and pulse rate will be permitted, as necessary, to ensure appropriate collection of safety data.

Supine BP will be measured with the subject's arm supported at the level of the heart, and recorded to the nearest mm Hg after approximately 5 minutes of rest. The same arm (preferably the dominant arm) will be used throughout the study. Subjects should be instructed not to speak during measurements.

The same properly sized and calibrated BP cuff will be used to measure BP each time. The use of an automated device for measuring BP and pulse rate is acceptable; however, when done manually, pulse rate will be measured in the brachial/radial artery for at least 30 seconds. When the timing of these measurements coincides with a blood collection, BP and pulse rate should be obtained prior to the nominal time of the blood collection.

7.1.4. Electrocardiogram

Triplicate 12-Lead ECGs should be collected at times specified in the **SCHEDULE OF ACTIVITIES** section of this protocol.

All scheduled ECGs should be performed after the subject has rested quietly for at least 10 minutes in a supine position.

Triplicate 12-lead ECGs will be obtained approximately 2 to 4 minutes apart; the average of the triplicate ECG measurements collected at pre-dose of Day 1 will serve as each subject's time-controlled baseline QTc value.

If the average of QTc values from the triplicate measurements remains above the threshold value (ie, is ≥ 45 msec from the baseline, or is ≥ 500 msec), then a single ECG must be repeated at least hourly until QTc values from 2 successive ECGs fall below the threshold value that triggered the repeat measurement.

If QTc values remain ≥ 500 msec (or ≥ 45 msec from the baseline) for greater than 4 hours (or sooner, at the discretion of the investigator), or QTc intervals get progressively longer, the subject should undergo continuous ECG monitoring. A cardiologist should be consulted if QTc intervals do not return to less than 500 msec (or to <45 msec above the baseline) after 8 hours of monitoring (or sooner, at the discretion of the investigator).

If subject develops new first degree block as defined by PR interval greater than 280 msec, if patient is found to have a second degree or higher AV block, or if patient has symptomatic bradycardia, patient should undergo continuous cardiac monitoring with 12-lead ECG taken every hour until PR interval returns to <220 msec, until AV block resolves or until symptoms resolve. If patient develops high degree AV block defined as second degree AV block, Mobitz II or third degree block, patient should be referred to a cardiologist for further evaluation.

In some cases, it may be appropriate to repeat abnormal ECGs to rule out improper lead placement as contributing to the ECG abnormality. It is important that leads are placed in the same positions each time in order to achieve precise ECG recordings. If a machine-read QTc value is prolonged, as defined above, repeat measurements may not be necessary if a qualified medical provider's interpretation determines that the QTc values are in the acceptable range.

7.2. Pharmacokinetics

7.2.1. Plasma for Analysis of Lorlatinib and Its Metabolite(s)

Plasma samples for characterization of PK of lorlatinib and its metabolite(s) will be collected at the designated times listed in **SCHEDULE OF ACTIVITIES** table.

In addition to samples collected at the scheduled times, an additional blood sample should be collected from patients experiencing unexpected and/or serious AEs and the date and time of blood sample collection and of last dosing prior to PK collection documented on the CRF.

The actual times may change, but the number of samples will remain the same. All efforts will be made to obtain the PK samples at the exact nominal time relative to dosing. However, samples obtained within 10% of the nominal time (eg, within 6 minutes of a 60-minute sample) from dosing will not be captured as a protocol deviation, as long as the exact time of the sample collection is noted on the source document and data collection tool (eg, CRF)

At each designated time, blood samples (8.0 mL) to provide approximately 3.5 mL plasma (aliquoted into 3 × 2 mL tubes, approximately 1.0 mL plasma in each tube) for determination of the plasma concentrations of lorlatinib and its potential metabolite(s) will be collected into appropriately labeled tubes containing dipotassium ethylenediaminetetraacetic acid (K₂EDTA). Details regarding the sample handling and shipping will be provided in the Lab Manual.

Lorlatinib is light sensitive; all steps must be performed out of direct light. It should be noted that once collected, samples should be processed immediately and kept out of direct light due to the light sensitive nature of lorlatinib. Once frozen, samples must not thaw, including during shipment.

- Samples will be analyzed for lorlatinib and metabolite(s) using a validated analytical method in compliance with Pfizer standard operating procedures (SOPs).
- The PK samples must be processed and shipped as indicated in the instructions provided to the investigator site to maintain sample integrity. Any deviations from the PK sample handling procedure (eg, sample collection and processing steps, interim storage or shipping conditions), including any actions taken, must be documented and reported to the sponsor. On a case-by-case basis, the sponsor may make a determination as to whether sample integrity has been compromised. Any deviation from the specified sample handling procedure resulting in compromised sample integrity will be considered a protocol deviation.
- As part of understanding the PK of the investigational product, samples may be used for metabolite identification and/or evaluation of the bioanalytical method, **CCI** [REDACTED] These data will not be included in the CSR.

7.2.2. Urine for Analysis of Lorlatinib

[figure not shown]
Urine will be collected at times specified in the **SCHEDULE OF ACTIVITIES** section of the protocol. Each subject will empty his or her bladder just prior to dosing.

Samples will be analyzed using a validated analytical method in compliance with Pfizer SOPs.

The PK samples must be processed and shipped as indicated in the instructions provided to the investigator site to maintain sample integrity. Any deviations from the PK sample handling procedure (eg, sample collection and processing steps, interim storage or shipping conditions), including any actions taken, must be documented and reported to the sponsor.

On a case-by-case basis, the sponsor may make a determination as to whether sample integrity has been compromised. Any deviation from the specified sample handling procedure resulting in compromised sample integrity will be considered a protocol deviation.

CCI

7.3. Pharmacogenomics

7.3.1. Genotyping Analysis (If Applicable; Pertains but is not Limited to Blood, Buccal Swabs, Saliva, and/or Tissue)

[figure not shown]
Blood samples for genotyping will be examined to assess the impact of allelic variants of drug-metabolizing enzymes and transporters. Additionally, these samples may also be used for retrospective evaluation of additional genetic variants associated with variation in PK or to explore AEs should these be observed. Samples will be retained for a period of up to 3 years after regulatory approval.

A 4-mL blood sample will be collected from each subject into a plastic K₂EDTA tube at times specified in the **SCHEDULE OF ACTIVITIES** section of the protocol.

[figure not shown]
Samples will be analyzed using a validated analytical method in compliance with Pfizer standard operating procedures

The pharmacogenomic (PGx) samples must be processed and shipped as indicated in the instructions provided to the investigator site to maintain sample integrity. Any deviations from the PGx processing steps, including any actions taken, must be documented and reported to the sponsor. On a case-by-case basis, the sponsor may make a determination as to whether sample integrity has been compromised. Any sample deemed outside of established stability, or of questionable integrity, will be considered a protocol deviation.

CCI

CCI

7.5. Blood Volume

The total blood sampling volume for individual subjects in this study is approximately 158 mL. The actual collection times of blood sampling may change. Additional blood samples may be taken for safety assessments at times specified by Pfizer, provided the total volume taken during the study does not exceed 550 mL during any period of 60 consecutive days.

7.6. Potential Cases of Acute Kidney Injury

Abnormal values in serum creatinine concurrent with presence or absence of increase in blood urea nitrogen (BUN) that meet the criteria below, in the absence of other causes of kidney injury, are considered potential cases of acute kidney injury and should be considered important medical events.

An increase of ≥ 0.3 mg/dL (or ≥ 26.5 μ mol/L) in SCr level relative to the subject's own baseline measurement should trigger another assessment of SCr as soon as practically feasible, preferably within 48 hours from awareness.

If the second assessment (after the first observations of ≥ 0.3 mg/dL (or ≥ 26.5 μ mol/L) in SCr relative to the subject's own baseline measurement) is ≥ 0.4 mg/dL (or ≥ 35.4 μ mol/L), the subject should be discontinued from the study and adequate, immediate, supportive measures taken to correct apparent acute kidney injury.

Subjects should return to the investigator site and be evaluated as soon as possible, preferably within 48 hours from awareness of the second assessment confirming abnormal SCr result. This evaluation should include laboratory tests, detailed history, and physical assessment. In addition to repeating SCr, laboratory tests should include serum BUN, serum creatinine kinase, and serum electrolytes (including at a minimum potassium, sodium, phosphate/phosphorus, and calcium), in addition to urinary dipstick, urine microscopic examination, and urinary indices. All cases confirmed on repeat testing as meeting the laboratory criteria for acute kidney injury, with no other cause(s) of laboratory abnormalities identified, should be considered potential cases of drug-induced kidney injury irrespective of availability of all the results of the investigations performed to determine etiology of the abnormal SCr. If ≥ 2 healthy subjects in any renal function group are noted to have 2 *consecutive* SCr results of ≥ 0.3 mg/dL (or ≥ 26.5 μ mol/L), an assessment of whether the finding may be considered an adverse drug reaction should be undertaken.

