3. STUDY DESIGN

3.1. Study Overview

This will be a Phase 1, open-label, multi-center, single treatment study in subjects with normal renal function and varying degrees of renal impairment. Each subject will receive a single oral dose of lorlatinib administered in the fasted state.

This study is aimed toward enrolling approximately 32 evaluable subjects who complete the PK assessments. Subjects with the following renal function will be enrolled (Table 4).

Table 4. Renal Function Groups

| Group (n) | Renal Function | eGFR |
|-----------|---------------------------|---------------------------------------|
| A (n=8) | normal | ≥90 mL/min |
| B (n=8) | mild renal impairment | ≥60 - <90 mL/min |
| C (n=8) | moderate renal impairment | ≥30 - <60 mL/min |
| D (n=8) | severe renal impairment | <30 mL/min and not requiring dialysis |

Subjects who do not complete all PK collections may be replaced to ensure 8 evaluable subjects in Groups A, B, and C and at least 4 evaluable subjects in Group D.

eGFR will be calculated using the Modification of Diet in Renal Disease (MDRD) equation as follows:

$$\text{eGFR (mL/min/1.73m}^2\text{)} = 175 \times (\text{S}_{\text{cr, std}})^{-1.154} \times (\text{Age})^{-0.203} \times (0.742 \text{ if female}) \times (1.212 \text{ if African American})$$

where $\text{S}_{\text{cr, std}}$ denotes serum creatinine measured with a standardized assay for serum creatinine. Note that the value of eGFR, which is directly obtained from the lab or calculated using the equation above, is generally normalized to an average body size of 1.73 m^2 for diagnosis, prognosis and treatment of renal disease. In terms of clearance of renally filtrated drugs (including secreted drugs), renal elimination capacity is related to absolute glomerular filtration rate (GFR) in mL/min. The MDRD-derived, body surface area (BSA)-adjusted value of eGFR used to obtain absolute GFR (mL/min) for renal disease classification or subject assignment into different renal disease groups should be multiplied by the individual subject's normalized body surface area (ie, measured BSA/ 1.73 m^2). The BSA of an individual can be calculated by the following formula as described below:

$$\text{BSA} = (\text{Weight}^{0.425} \times \text{Height}^{0.725}) \times 0.007184$$

In addition CL_{cr} will be calculated using the Cockcroft-Gault equation as follows:

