$$CL_{cr} (\text{mL/min}) = \frac{[140 - \text{age (years)}] \times \text{total body weight (kg)} \times (0.85 \text{ for females})}{72 \times \text{serum creatinine (mg/dL)}}$$

Subjects will need to demonstrate stable renal function during the screening period within approximately a 2-week timeframe prior to dosing. Stable renal function is defined as 2 eGFR values obtained at least 3 days but not more than 14 days apart being within 25% of each other. The average value of the 2 eGFR values will be used for study enrollment and initial renal function stratification. The SCr value used to calculate eGFR collected within 24 hours prior to lorlatinib dosing will be the value used for final subject stratification, group assignment, and PK analysis. The CL_{cr} value will be recorded at the same time eGFR is determined. The CL_{cr} value on Day -1 (calculated by Cockcroft-Gault equation) will be calculated and recorded.

In order to safeguard subject safety, this study will enroll subjects with renal impairment in a staggered fashion. A single oral dose of 100 mg lorlatinib will be administered first to subjects with mild renal impairment (Group B). After single 100 mg oral dose of lorlatinib is tolerated in at least 3 subjects with mild renal impairment, subjects with moderate renal impairment (Group C) will be enrolled one at a time and administered a single oral dose of lorlatinib. There will be an observation period of at least 1 week after dosing of the first 3 subjects to evaluate safety and tolerability. Based on the safety and tolerability of the first 3 subjects in Group B, a dose lower than 100 mg of lorlatinib may be considered for Group C, as determined by the Sponsor. After dosing of 3 moderate renal impairment subjects, the PK, safety, and tolerability will be evaluated during an observation period of at least 1 week to confirm whether the selected dose is appropriate. If yes, the remaining subjects in Group C and the subjects in severe group (Group D) will be enrolled and dosed at the same dose. If not, a new, lower dose will be proposed for the remaining subjects in Group C and all subjects in Group D based on available information.

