4.1.1. All Subjects

1. Healthy (with the exception of defined renal impairment as described above in [Section 3](#)) female subjects of non-childbearing potential and/or male subjects who, at the time of screening, are between the ages of 18 and 75 years, inclusive. Healthy is defined as no clinically relevant abnormalities identified by a detailed medical history, full physical examination, including blood pressure (BP) and pulse rate measurement, 12-lead ECG, or clinical laboratory tests.

Female subjects of non-childbearing potential must meet at least 1 of the following criteria:

- a. Achieved postmenopausal status, defined as follows: cessation of regular menses for at least 12 consecutive months with no alternative pathological or physiological cause; and have a serum follicle-stimulating hormone (FSH) level confirming the postmenopausal state;

- b. Have undergone a documented hysterectomy and/or bilateral oophorectomy;
- c. Have medically confirmed ovarian failure.

All other female subjects (including female subjects with tubal ligation) are considered to be of childbearing potential.

2. Body mass index (BMI) of 17.5 to 36 kg/m²; and a total body weight >50 kg (110 lb).
3. Evidence of a personally signed and dated informed consent document indicating that the subject has been informed of all pertinent aspects of the study.
4. Subjects who are willing and able to comply with all scheduled visits, treatment plan, laboratory tests, and other study procedures.

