6.2.1. Day -1

Subjects will be admitted to the CRU on Day -1 prior to Day 1 dosing. The following procedures will be completed following admission to the CRU:

- Review inclusion and exclusion criteria.

- Obtain blood and urine samples for safety laboratory tests (hematology, clinical chemistry, urinalysis) after overnight fast. The results must have no clinically significant findings, as judged by the Investigator, in order for a subject to be given investigational product on Day 1.
- Obtain weight.
- Collect urine for drug testing (mandatory) and alcohol breath test at discretion of the Investigator. These tests may be performed at any other time at the discretion of the investigator.
- The investigator or his/her designee will discuss with the subject the need to use highly effective contraception consistently and correctly according to the contraception guidelines and will confirm highly effective contraception is being used.
- Serum creatinine, eGFR, and creatinine clearance calculation.
- Collect triplicate 12-lead ECG.
- Obtain single supine BP and pulse rate pulse rate after at least 5 minutes of rest in a supine position.
- Collect **CCI** [REDACTED] a blood sample for pharmacogenomics on Day -1. **CCI** [REDACTED]
- Assess baseline symptoms/AEs.
- Review prior and concomitant medication(s).
- Review changes in the subject's medical history, including medication history since Screening.
- Conduct full PE, if deferred from the Screening visit. A limited PE may be performed at other designated time points at the discretion of the investigator.

6.2.2. Day 1

Prior to lorlatinib dosing, the following procedures will be completed:

- Assess baseline symptoms/AEs.
- Collect triplicate 12-lead ECG measurements prior to insertion of the IV catheter.
- Collect supine BP and pulse rate prior to insertion of the IV catheter.

- Collect blood samples for PK analysis of lorlatinib and its metabolite(s).
- Collect a blank urine sample of at least 50 mL for all subjects. Each subject will empty his or her bladder just prior to dosing.
- After all pre-dose procedures have been completed, administer the investigational product (see [Section 5.4](#)).

After dosing, the following procedures will be completed:

- Subject should be supine for at least 10 minutes prior to triplicate 12-lead ECG measurements at 1, 2, 4 hours after dosing.
- Assess supine BP and pulse rate at 1, 2, and 4 hours after dosing.

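### Protocol 7.6 omits the words for an increase from baseline at two creatinine limits, so a repeat value back at baseline still meets the discontinuation limit: a minor wording error in a safety rule

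*Protocol*

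**What the plan says.** Protocol Section 7.6 contains three creatinine limits.

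- **First trigger.** An increase of at least 0.3 mg/dL (26.5 µmol/L) relative to the subject's "own baseline measurement should trigger another assessment of SCr as soon as practically feasible, preferably within 48 hours from awareness".
- **Discontinuation limit.** If the second assessment is at least 0.4 mg/dL (35.4 µmol/L), "the subject should be discontinued from the study and adequate, immediate, supportive measures taken to correct apparent acute kidney injury". The reference to baseline in this sentence stands inside a parenthesis that describes the first observation. It is not attached to the 0.4 limit.
- **Cluster rule.** If at least two "healthy subjects in any renal function group are noted to have 2" consecutive creatinine results of at least 0.3 mg/dL, the finding is assessed as a possible adverse drug reaction. This sentence mentions neither an increase nor a baseline.

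Between the second and third limits, the section asks for an evaluation "preferably within 48 hours from awareness of the second assessment confirming abnormal SCr result".

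Section 7.6 does not say which pre-dose creatinine is the baseline. SAP Section 8.3.5 defines the laboratory baseline as the last planned pre-dose measurement. By Protocol Section 6.2.1 that is Day -1, where the list includes "Serum creatinine, eGFR, and creatinine clearance calculation". No other part of the Protocol or SAP restates or corrects the three limits.

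**The concern.** The repeat exists to separate a confirmed rise from a false alarm. A confirmation limit written as a concentration does this only if some subjects without a persisting rise fall below it. A limit of 0.4 mg/dL is lower than the creatinine of almost any adult, and certainly of adults enrolled for renal impairment. A repeat back at baseline therefore meets the limit and confirms nothing. The same holds for the 0.3 mg/dL cluster limit.

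Sites in a multi-center study apply this rule directly. The first scheduled post-dose creatinine is at 24 hours (Section 6.2.3), with PK samples still due at 48, 72, 96 and 120 hours. If the text is followed exactly, a subject with a transient rise at 24 hours that resolves on repeat is discontinued and may lose some of those samples.

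Other safety rules in the protocol attach the baseline to the limit itself. Examples are the QTc rule in Section 7.1.4 and the bilirubin rule in Section 8.4.1.

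**Working it through.** **Printed unit pairs.** With 88.4 µmol/L per mg/dL (the printed pairs imply 88.3 to 88.5):
- 0.3 × 88.4 = 26.52, printed 26.5.
- 0.4 × 88.4 = 35.36, printed 35.4.

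Both reproduce, so the thresholds contain no numerical slip.

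**Inputs**
- MDRD and BSA formulas and group limits: Protocol 3.1. The BSA-adjusted value is multiplied by BSA/1.73 and "used to obtain absolute GFR (mL/min) for renal disease classification or subject assignment into different renal disease groups".
- Age 18 to 75 years, BMI 17.5 to 36 kg/m², weight above 50 kg (50 used as the boundary): Protocol 4.1.1.
- Final assignment: "The SCr value used to calculate eGFR collected within 24 hours prior to lorlatinib dosing will be the value used for final subject stratification".

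**Formula.** Solving MDRD for creatinine, with sex = 0.742 for women and 1 for men:

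SCr = [(eGFR_abs × 1.73/BSA) / (175 × age^-0.203 × sex)]^(-1/1.154)

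The race factor is set to 1, because the factor 1.212 only raises SCr.

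**Lowest creatinine compatible with Groups B, C and D.** The minimum over the eligible range is a woman aged 75 weighing 50 kg with BMI 36:
- Height = √(50/36) = 1.179 m.
- BSA = 0.007184 × 50^0.425 × 117.9^0.725 = 1.203 m².
- Denominator = 175 × 0.4163 × 0.742 = 54.05.

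| Upper group limit (mL/min) | Indexed eGFR | Extreme corner | Woman 75, 50 kg, 150 cm (BSA 1.433) | Woman 60, BSA 1.73 | Man 60, BSA 1.73 |
|---|---|---|---|---|---|
| B: 90 | 129.5 | 0.469 | 0.546 | 0.67 | 0.87 |
| C: 60 | 86.3 | 0.667 | 0.776 | 0.95 | 1.23 |
| D: 30 | 43.2 | 1.215 | 1.414 | 1.73 | 2.24 |

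The indexed eGFR column belongs to the extreme corner, and the last four columns are SCr in mg/dL. Each value is the lowest in its group for that profile, because lower eGFR means higher creatinine. All 24 planned impaired subjects (3 × 8) are therefore above 0.4 mg/dL at baseline.

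**Group A.** Absolute eGFR at a given creatinine = 175 × SCr^-1.154 × age^-0.203 × sex × BSA/1.73.

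| SCr (mg/dL) | Woman 60, BSA 1.73 | Man 60, BSA 1.73 | Woman 75, 50 kg, 150 cm |
|---|---|---|---|
| 0.4 | 162.8 | 219.4 | 128.8 |
| 0.3 | 226.9 | 305.8 | 179.6 |

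A Group A subject escapes the literal 0.4 limit only at an eGFR (mL/min) above the figures in the first row, and the literal 0.3 limit only above those in the second.

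**What each reading does after a first rise of at least 0.3 mg/dL.** Take a man aged 60, BSA 1.73, whose repeat is exactly at baseline:

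| eGFR | Baseline = repeat | Repeat needed, as a level | Repeat needed, as a rise |
|---|---|---|---|
| 90 | 0.87 | 0.40 (met) | 1.27 (not met) |
| 60 | 1.23 | 0.40 (met) | 1.63 (not met) |
| 30 | 2.24 | 0.40 (met) | 2.64 (not met) |

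Read as a level, the cluster limit is met by ordinary values in every group.

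**Samples at risk.** If the 24-hour result is known at once and the repeat takes the preferred maximum of 48 hours, it falls at 24 + 48 = 72 hours. A quicker repeat puts more of the 48 to 120 hour samples at risk. Cmax is already observed by then: Section 1.3.1.1.1 gives a median time to peak of 1 to 2 hours.

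**The case against.** The strongest reply is that the text is shorthand rather than error. The section opens with an increase from baseline. The parenthesis in the 0.4 sentence again gives a bare figure relative to baseline where a rise is plainly meant. The cluster sentence reuses the pair 0.3 mg/dL and 26.5 µmol/L already introduced as an increase. A clinician is unlikely to take 0.4 mg/dL as an injury threshold in subjects with eGFR below 30. This stands as evidence of intent and is why the point is minor. It does not make the wording correct.

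A reader might infer that subjects with no rise could be discontinued, since nearly everyone is above 0.4 mg/dL. The documents do not support this: the second assessment exists only after a documented rise of at least 0.3 mg/dL from baseline.

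The consequence is also small. Each subject receives one dose, so discontinuation withholds no treatment. The early-withdrawal visit includes safety laboratory tests and a PK sample (Section 6.5), and subjects with incomplete PK collection may be replaced (Sections 3.1 and 9.1). The cluster rule leads only to an assessment.

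The benefit of rewording has a limit too. A 25% fall in eGFR, which the stability criterion allows, is a creatinine rise of 0.75^(-1/1.154) − 1 = 28%, or about 0.64 mg/dL at 2.24 mg/dL. Even as rises, limits of 0.3 and 0.4 are only about 13% and 18% of that baseline. The correction makes the rule say what it means, but does not make it specific in Group D.

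**Conclusion.** The point holds as a minor wording error in an operative safety rule. Section 7.6 omits the increase from baseline at the 0.4 mg/dL discontinuation limit and at the 0.3 mg/dL cluster limit. Read literally, a subject who has already had a first rise is discontinued even when the repeat is back at baseline, and the cluster limit is met by ordinary creatinine values.

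The literal error over-triggers and cannot miss a true rise. No frequency of wrong discontinuation is claimed, because a rise is evidently intended and the documents give no rate of transient rises.

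A reader might also infer that the primary comparison is compromised. It is not: the rule plays no part in defining AUCinf or Cmax, and the effect is limited to possible loss of later PK samples in a subject with a transient rise. Nor is baseline undefined for the study, since SAP 8.3.5 with the schedule points to Day -1. The gap in 7.6 is only a missing cross-reference.

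The creatinine figures rest on the protocol's MDRD and BSA formulas and its eligibility limits. The lowest values come from a deliberately extreme body size (118 cm, 50 kg), and every more typical profile lies further above the limits.

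**What to change.** Change two phrases in Protocol Section 7.6:

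- Discontinuation limit: *second assessment shows an increase of ≥0.4 mg/dL (≥35.4 µmol/L) relative to the subject's own baseline*.
- Cluster rule: *2 consecutive SCr results showing an increase of ≥0.3 mg/dL (≥26.5 µmol/L) relative to baseline*.

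Optionally, add a clause naming the Day -1 creatinine as baseline, in line with SAP 8.3.5.

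The cost is two phrases and, if wanted, one clause. Thresholds, procedures, sample size and analyses do not change. Whether PK and urine collection should continue after a confirmed rise is a clinical decision for the sponsor and is not part of this point.
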